5.5. Procedures for Withdrawal or Discontinuation

The efficacy and safety examinations to be completed upon study withdrawal as specified in the protocol must be completed as much as possible. In addition, the safety follow-up should be completed along with fully documented AEs and their outcomes. The investigators can recommend or provide new or alternative treatments to a subject based on the condition of the subject. Subjects showing no PD need to be continuously followed-up for imaging evaluation until the subjects begin new anti-tumor treatment or show PD.

Subject's survival status should still be followed up even when the subject refuses to visit study sites, unless the subject withdraws consent to provide further information or consent to be further contacted. In such case, no study assessment is performed, nor any data are collected.

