8.6. Criteria for Continuing Treatment Beyond Progression

Some subjects receiving immunotherapy can still benefit clinically after radiographic progression. The study treatment may be continued after PD defined per Lugano 2014 criteria for subjects who meet the criteria below:

- The investigators deem that it is in the best interest of the subject to continue treatment, and subject is not required to start other anti-tumor treatment immediately;
- The subject is able to tolerate continued study treatment
- No significant deterioration in subject's performance status, and no significant worsening of cancer-related symptoms
- Before continuing the study treatment, it must be reviewed and approved by the medical monitor

If it is decided that the subject will continue the study treatment after progression, the subject should continue to be treated, evaluated, and followed up according to the protocol requirements.

Subjects should withdraw from study treatment if further progression is observed at the next assessment. The initial date of investigator-assessed progression should be used for all statistics analyses involving progression, regardless of whether the subject continues the study treatment beyond progression.

If the subject discontinues treatment due to deterioration of the general condition without objective evidence for PD, the progression will be reported as "general deterioration". More objective evidences (such as imaging confirmation) of progression of these subjects should be obtained after treatment discontinuation.

For subjects who withdraw from the study due to intolerable toxicity without radiographic PD observed, the imaging examination should be performed at the same frequency, until PD or start of other anti-tumor treatment. The radiographic evidence of PD of these subjects must be obtained whenever possible.

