9. ASSESSMENTS

9.1. Assessment of Efficacy

The Lugano 2014 criteria are used to evaluate the objective response rate (ORR), including the CR and PR cases.

ORR: Defined as the proportion of subjects whose best response reaches CR or PR from the first dose to the occurrence of PD or the start of new anti-tumor treatment, whichever comes first

PFS: Defined as the time from the date of the first dose to the first documented PD or all-cause death, whichever occurs first. If the subject has not had PD or died by the data cut-off date, the cut-off date is the date of the subject's last efficacy evaluation. If the subject has not received tumor evaluation, the cut-off date is the date of the first dose, and PFS lasts for 1 day.

DoR: Defined as the time from the date of the first CR or PR to the date of initial assessment of PD or all-cause death, whichever comes first. If the subject has not had PD or died by the data cut-off date, the censoring date is the date of the subject's last efficacy evaluation. Only applicable to subjects with CR/PR.

TTR: Defined as the time from D1 of administration to the first evaluation of PR or CR, whichever comes first. Only applicable to subjects with CR/PR.

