8. APPENDIX

Appendix 1.1. Definition of progression-free survival (PFS).

No.	Situation	Date of Progression/ Censoring	Handling
1	No baseline assessment	Date of first dose	Censoring
2	No post-baseline assessment, and no death	Date of first dose	Censoring
3	Any death (except #5)	Date of death	Event
4	Progressive disease during study (including after missing one assessment)	Date of progressive disease	Event
5	Death or progressive disease after 2 consecutive missing tumor assessments	Date of last tumor assessment before missing	Censoring
6	Withdrawal from the study due to toxicity or other reasons without PD or death record	Date of last tumor assessment before study withdrawal	Censoring
7	No progressive disease or death recorded before the initiation of new anti-cancer treatment	Date of last recorded objective tumor assessment as no PD before the initiation of new anti-tumor treatment	Censoring

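### PFS censoring row 6 in the SAP can be applied to subjects the protocol keeps scanning after a toxicity withdrawal; if it is, later clean scans are dropped while later progressions and deaths count, so PFS can only stay equal or fall

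*SAP*

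**What the plan says.** **SAP Appendix 1.1 (PFS).** Row 6 applies to "Withdrawal from the study due to toxicity or other reasons without PD or death record". The subject is censored, and the date is "Date of last tumor assessment before study withdrawal". Row 4 makes progression during the study an event on its own date, including after one missed assessment. Row 3 makes every death an event except those in row 5 (after two consecutive missed assessments). Row 7 deals with new anti-cancer treatment.

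**Protocol Section 8.6.** "For subjects who withdraw from the study due to intolerable toxicity without radiographic PD observed, the imaging examination should be performed at the same frequency", and this continues until PD or other anti-tumor treatment.

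**Protocol Section 5.5**, which covers both withdrawal and discontinuation: "Subjects showing no PD need to be continuously followed-up for imaging evaluation until the subjects begin new anti-tumor treatment or show PD". Data collection ends only when the subject withdraws consent to give information or to be contacted.

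**Protocol Section 8.4.** Subjects who stop treatment for reasons other than PD stay on the tumor assessment schedule.

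**Protocol Section 9.1 (PFS).** "If the subject has not had PD or died by the data cut-off date, the cut-off date is the date of the subject's last efficacy" assessment. Nothing there cuts follow-up at withdrawal. DoR has its own censoring rule in the same section, also at the last efficacy evaluation.

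**The concern.** Row 6 and Section 8.6 describe what looks like one group: out of the study for toxicity, with no PD. The protocol keeps scanning that group. Row 6, read literally, ends their PFS follow-up at the last scan before they left.

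Take two subjects who withdraw for toxicity at month 6 in the sense of Section 8.6 and are scanned to month 24, with no new treatment and no missed scans. One progresses at month 20. That subject has a PD record, so row 6 does not apply and row 4 gives an event at month 20. The other is PD-free throughout, meets row 6, and is censored at or before month 6. Whether the time after withdrawal is used depends on how it turned out. Kaplan-Meier assumes that censoring carries no such information.

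At stake are the PFS curve, its median and its rates, which are secondary results. Scans that the protocol requires would be collected and then not used, and the SAP would depart from the protocol's own PFS definition.

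**Working it through.** **The plan's own figure.** Neither document states a PFS median, rate, event count or power, so there is none to reproduce.

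**Step 1: direction.** Each Kaplan-Meier factor is 1 − d/n, with d events among n at risk. Compared with Section 9.1, row 6 leaves every event in place on the same date, because a subject with PD or death on record is not in row 6. It only removes event-free subjects earlier. So d is unchanged and n is equal or smaller at every event time. Each factor is equal or smaller, and so is the curve. No assumption about rates is needed.

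**Step 2: size.** Inputs:
- From the documents: enrollment June to November 2017 (5 months) and study end 24 months after the last first dose, so follow-up C is about 24 to 29 months; 60 subjects.
- Assumed: exponential PFS with median m = 12, 18 or 24 months; independent non-PD withdrawal with 12-month probability p = 5, 10 or 15%; full scanning afterwards; no new therapy; C uniform; censoring at the withdrawal date itself as an approximation to the last scan before it.

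Let λ = ln 2/m, ω = −ln(1 − p)/12, S(t) = exp(−λt), and S_C = the mean of S(C).
- At risk under Section 9.1: S(t).
- At risk under row 6: R(t) = S(t) − S_C × (1 − exp(−ωt)). The subtracted part is subjects who withdrew before t and are PD-free at cut-off.
- PFS under row 6 at 24 months: exp(−∫ λS(t)/R(t) dt), integrated from 0 to 24.

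Example, m = 24 and p = 10%: S(24) = 0.500, S_C = 0.466, 1 − 0.9² = 0.19. R(24) = 0.500 − 0.466 × 0.19 = 0.411, so the apparent hazard at month 24 is 0.500/0.411 = 1.22 times the true one. Integrated over 24 months, PFS is 47.2% instead of 50.0%.

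| Assumed median | True 24-month PFS | Row 6, p = 5% | p = 10% | p = 15% | Fall (points) |
|---|---|---|---|---|---|
| 12 months | 25.0% | 24.0% | 22.9% | 21.8% | 1.0 to 3.2 |
| 18 months | 39.7% | 38.4% | 37.0% | 35.6% | 1.3 to 4.1 |
| 24 months | 50.0% | 48.7% | 47.2% | 45.7% | 1.3 to 4.3 |

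The expected number censored early is 60 × the mean of S(C)(1 − exp(−ωC)), which runs from 1.4 to 8.4 subjects. A simulation on the same assumptions gave the same falls, with about 14 months of PD-free follow-up lost per affected subject.

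**Step 3: the protocol's scan schedule.** A simulation used the planned scan weeks, 5-month accrual and at least 24 months of follow-up. It gave PFS at 22.5 months, Section 9.1 rule against row 6:
- Median 12 months: 28.0% against 26.8% (5% withdrawal per year); 28.0% against 25.5% (10%).
- Median 24 months: 52.8% against 51.4% (5%); 53.0% against 50.0% (10%).

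The estimated median moved only with an assumed median of 24 months and 10% or more withdrawal, by one scheduled scan (28.1 to 22.1 months). At 30% per year, well outside the range in step 2, the largest fall was 10.5 points.

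**Step 4: is the asymmetry the cause?** When PD after withdrawal was ignored as well, the difference vanished (28.0% against 27.9% with median 12 months and 10% per year).

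**Step 5: primary analysis.** It takes place when the last subject has had 6 months of treatment, so follow-up is about 6 to 11 months. The step 2 formula at t = 6, with C uniform on 6 to 11, gives a fall of 0.2 to 0.8 points.

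**The case against.** The strongest reply is that study withdrawal is not the same as stopping treatment. Protocol Sections 5.3 and 5.4 list them separately, and SAP Section 5.2.1 distinguishes them. Under Section 8.4, a subject who stops treatment for toxicity is in progression follow-up and so still in the study. On that reading row 6 reaches only those who have left altogether. They have no later scans, and row 6 then gives the same date as Section 9.1. This reading is plausible, and it stands as a possibility. It is not secured by the text: Section 8.6 says "For subjects who withdraw from the study due to intolerable toxicity without radiographic PD observed" and then requires imaging, Section 5.3 lists adverse reactions among the reasons for study withdrawal, and Section 5.5 covers withdrawal and discontinuation together.

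A second reply is that row 4 requires progression during the study, so PD after withdrawal might not count either. The SAP does not say so. If it were so, the PD part of the asymmetry would go, but deaths would still count under row 3.

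Third, the rates are assumed, and rows 5 and 7 would censor some later events and shrink the effect. This is correct. For scale, a binomial 95% interval around 50% with 60 subjects has a half-width of 1.96 × √(0.25/60) = 12.7 points, so a fall of 1 to 4 points is small beside sampling error. It is, however, a fall in a known direction, and it can be avoided.

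**Conclusion.** The point holds conditionally. If row 6 is applied to subjects who keep being scanned, as its wording and Section 8.6 allow, PFS is biased downward or unchanged. If it is limited to subjects with no further follow-up, nothing is lost. The direction is certain under the first reading. The size, about 1 to 4 points on 24-month PFS, rests on the assumed PFS distribution, withdrawal rates, complete later scanning and 24-29 months of follow-up. It is smaller at the primary analysis and where rows 5 or 7 apply.

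Three stronger inferences are not supported:
- *Clean scans will certainly be discarded.* The documents allow this but do not settle it. In particular, someone who only stops treatment is still in progression follow-up under Section 8.4.
- *DoR inherits the rule.* Appendix 1.1 is titled for PFS, and Section 9.1 gives DoR its own censoring at the last efficacy evaluation.
- *The trial's conclusion is at risk.* PFS is secondary, with no hypothesis attached. The decision rule uses ORR alone, and any bias here works against the drug.

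The SAP should still be corrected, because one row as written can give a result that conflicts with the protocol's definition.

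**What to change.** Reword row 6 so that a subject without PD or death is censored at the last evaluable tumor assessment without PD before data cut-off, or before new anti-tumor treatment under row 7, whether or not the subject has stopped treatment or withdrawn. Keep the cut at withdrawal only for subjects who withdrew consent to further assessment or were lost to follow-up. State that DoR follows Section 9.1 and that row 6's cut at withdrawal does not apply to it. With the results, report how many subjects in row 6 had a tumor assessment after their withdrawal date, which shows directly whether the issue arose.

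The cost is one row and one sentence in the SAP. The scans are already required. The change brings row 6 back to Section 9.1, so it does not by itself call for a protocol amendment.
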